# 6.4 PROCEDURES FOR ASSESSING SAFETY, ADHERENCE AND OTHER TRIAL EVENTS

Aspirin toxicity and adverse events will be assessed and documented at each follow-up assessment using CTCAE v4 in addition to expedited reporting of SAEs (see section 7).

Participant self-reported adherence, as well as concomitant medications, will be documented on CRFs at each follow-up assessment. Blood tests will be performed at some visits, including a fasting sample at the time of registration. Blood pressure and weight will also be checked.

In order to facilitate an assessment of the overall impact of aspirin on health outcomes, the occurrence of key events/diagnoses (including vascular events, thrombotic events, diabetes and associated complications, dementia, and age-related macular degeneration) will be documented on Non-Cancer Event CRFs (Form 10).

Where a trial visit is additional to local standard care, assessments can be conducted via telephone follow-up providing that all the required information can be obtained, and appropriate measures for dispensing trial medications are made. A subset of participants may also be asked if they would agree to participate in a sub-study directly reporting trial-related outcomes through a web-based system.

# 6.5 CHARLSON COMORBIDITY INDEX

The presence of comorbidities will be assessed using the Charlson Comorbidity Index. This 22-item questionnaire will be performed once at trial registration. It illustrates the extent to which a patient suffers from common comorbidities. Patients are assessed for the presence of various comorbidities, with points allocated to each comorbidity if the condition is present. Points range from 1 to 6, with greater weighting given to items that are considered more serious. The final score is a weighted co-morbidity score and is calculated as the total number of points allocated for the patient.

# 6.6 VULNERABLE ELDERS SURVEY (VES-13) FOR UK AND REPUBLIC OF IRELAND ONLY

Functional capacity will be assessed using the VES-13. This will be performed for participants that are 65 years old or over at trial registration, both at registration and 5 years after randomisation. This 13-item, self-reported questionnaire (Functional Status CRF (Form 5)) can be administered in person or via the telephone, and assesses vulnerability across four domains: age, health in comparison to others, physical function and functional disability. The survey has a maximum final score of 10, with an upper limit put on the number of points awarded for each domain. The VES-13 survey will allow an investigation of the overall health benefits of aspirin in older people.

The VES-13 will not be performed in India due to the lack of validated translations; this will not affect the safety of the patients nor the required efficacy assessments.

# 6.7 COGNITIVE ASSESSMENT USING THE MOCA-BLIND FOR UK AND REPUBLIC OF IRELAND ONLY

The hypothesis that aspirin protects against cognitive decline will be assessed using a short version of the Montreal Cognitive Assessment (the MoCA-blind). This short questionnaire (Cognitive Assessment CRF (Form 6)) tests cognitive functioning across five domains: attention, language, abstraction, memory recall and orientation. The MoCA-blind takes approximately ten minutes to complete and will be administered in all Add-Aspirin participants at registration, then again at one and five years after randomisation. No formal training is required to administer the questionnaire – instructions are included as part of the CRF (and an audio recording of the questionnaire being administered is available on the website, addaspirintrial.org). It can be administered by a non-clinical member of staff (for example, a Data Manager), providing that delegation of the task is appropriately documented on the delegation log. The questionnaire can also be administered over the phone where no clinic visit is planned.

The cognitive assessment will not be performed in India due to the lack of validated translations; this will not affect the safety of the patients nor the required efficacy assessments.

# 6.8 EXERCISE QUESTIONNAIRE

The measurement of physical activity levels in Add-Aspirin participants across 4 tumour sites will investigate the association between physical activity and cancer and non-cancer outcomes. The International Physicial Activity Questionnaire (IPAQ) takes approximately five minutes and will be administered in all Add-Aspirin participants at one and five years after randomisation. It is included in the Follow Up CRF (Form 8) and can be administered by a non-clinical member of staff (for example, a Data Manager) as part of the follow up visit or can be self-administered by the

participant. To address cultural differences, the examples of exercise given in the IPAQ have been modified to suit Indian participants' understanding of exercise efforts.

# 6.9 EARLY STOPPING OF FOLLOW-UP

If trial treatment is discontinued, for whatever reason, this should be documented on the relevant CRF. During the run-in this should be recorded on the End of Run-in CRF (Form 7). During the randomised phase this should be recorded on an Early Cessation of Trial Treatment CRF (Form 12). If discontinuation during the randomised phase is caused by an aspirin related toxicity, a Notable Event CRF (Form 11) should be submitted. Following discontinuation of trial treatment the participant should continue to be followed up, providing they are willing. That is, they should be encouraged not to withdraw from the trial completely; if they do not wish any further follow-up data to be collected, their decision must be respected and the participant will be withdrawn from the trial completely. The MRC CTU at UCL should be informed of this by email, and receipt will be confirmed. Participants stopping follow-up early have a negative impact on trial data, so this should be avoided where possible.

Consent for future use of stored samples already collected can be withdrawn when leaving the trial early (and this should be indicated when notifying the CTU of the withdrawal), but this should be discussed with the participant and avoided where possible.

If participants change their minds about stopping trial follow-up at any time, please contact MRC CTU at UCL to discuss re-enrolment.

Participants who stop trial follow-up early will not be replaced, but the sample size allows for a degree of loss to follow-up.

Participants in the UK will be followed up in the long-term through NHS electronic data records available, which will include flagging with the NHS Information Centre and other national registries and healthcare databases (see section 9.3.1). Consent for this aspect of follow-up should be indicated on the Consent Form at the time of registration and the MRC CTU at UCL should be informed in writing if the participant later wishes to withdraw consent, but this should be discussed with the participant and avoided where possible. In order to collect long-term follow-up data in India and Republic of Ireland, participants will be contacted on an annual basis for a further 5 years.

In all countries, every effort should be made by Investigators to follow-up participants on a longterm basis. For participants who stop follow-up early, data collected up to the time of withdrawal from follow-up will be kept and included in the analysis unless the participant explicitly withdraws consent for this. For further information relating to withdrawal please refer to the Withdrawal Guidance Document.

# 6.10 PARTICIPANT TRANSFERS

If a participant moves from the area, every effort should be made for them to be seen at another participating trial centre, and this should be discussed with the MRC CTU at UCL at the earliest opportunity. A patient transfer form should be completed by both the old and new site to confirm the transfer. A copy of the participant's CRFs should be provided to the new centre and the participant will need to sign a new Consent Form. Once this has been done, the new centre will take over responsibility for the participant within the trial; until this has been done, responsibility for the participant lies with the original centre.

Where centres are participating in screening for the POLEM trial, but are not participating fully in that trial, patients will normally transfer to a nearby POLEM centre to receive POLEM treatment and will subsequently transfer back to the original Add-Aspirin centre for recruitment into Add-Aspirin if relevant. Please see Appendix XIV for details.

# 6.11 TRIAL CLOSURE

The trial will be considered closed approximately 10 years after the last participant was randomised, when all participants have completed follow-up in the trial.

# 7 SAFETY REPORTING

The principles of ICH GCP require that both Investigators and sponsors follow specific procedures when notifying and reporting adverse events or reactions in clinical trials. These procedures are described in sections 7.1-7.4.

# 7.1 **DEFINITIONS**

The definitions of the EU Directive 2001/20/EC Article 2 based on the principles of ICH GCP apply to this trial protocol. These definitions are given in table 5.

Table	5:	Definitions
IUNIC	٠.	Dermitions

TABLE	DEFINITION	
Adverse Event (AE)	Any untoward medical occurrence in a patient or clinical trial participant to whom a medicinal product has been administered including occurrences that are not necessarily caused by or related to that product.	
Adverse Reaction (AR)	Any untoward and unintended response to an investigational medicinal product (IMP) related to any dose administered.	
Unexpected Adverse Reaction (UAR)	An adverse reaction, the nature or severity of which is not consistent with the information about the medicinal product in question set out in the Summary of Product Characteristics (SPC) for that product.	
Serious Adverse Event (SAE) or Serious Adverse Reaction (SAR) or Suspected Unexpected Serious Adverse Reaction (SUSAR)	
 
Respectively any adverse event, adverse reaction or unexpected adverse reaction that:
 
Results in death
 
Is life-threatening*
 
Requires hospitalisation or prolongation of existing hospitalisation**
 
Results in persistent or significant disability or incapacity
 
Consists of a congenital anomaly or birth defect
 
Is another important medical condition***
 
	

\*The term life-threatening in the definition of a serious event refers to an event in which the participant is at risk of death at the time of the event; it does not refer to an event that hypothetically might cause death if it were more severe, for example, a silent myocardial infarction.

\*\*Hospitalisation is defined as an inpatient admission, regardless of length of stay, even if the hospitalisation is a precautionary measure for continued observation. Hospitalisations for a pre-existing condition (including elective procedures that have not worsened) do not constitute an SAE.

\*\*\* Medical judgement should be exercised in deciding whether an AE or AR is serious in other situations. The following should also be considered serious: important AEs or ARs that are not immediately life-threatening or do not result in death or hospitalisation but may jeopardise the subject or may require intervention to prevent one of the other outcomes listed in the definition above; for example, a secondary malignancy, an allergic bronchospasm requiring intensive emergency treatment, seizures or blood dyscrasias that do not result in hospitalisation or development of drug dependency.

# 7.1.1 MEDICINAL PRODUCTS

An IMP is defined as the tested investigational medicinal product and the comparators used in the study. (EU guidance ENTR/CT 3, April 2006 revision). In Add-Aspirin, aspirin and the placebos are IMPs, including the aspirin used during the run-in period.

Adverse reactions include any untoward or unintended response to drugs. Reactions to an IMP should be reported appropriately.

# 7.1.2 CLARIFICATIONS AND EXCEPTIONS

Adverse Events include:

- An exacerbation of a pre-existing illness
- An increase in frequency or intensity of a pre-existing episodic event or condition
- A condition (even though it may have been present prior to the start of the trial) detected after trial drug administration
- Continuous persistent disease or a symptom present at baseline that worsens following administration of the study treatment

# 7.1.3 EXEMPTED ADVERSE EVENTS

The following events, in the context of this trial, do not require reporting on Serious Adverse Event (SAE) forms.

- Medical or surgical procedures; the condition that leads to the procedure is the adverse event
- Hospitalisations where no untoward or unintended response has occurred, e.g. elective cosmetic surgery, social admissions
- Grade 1 events and grade 2 events where there are no clinical symptoms

# 7.2 OTHER NOTABLE EVENTS

# 7.2.1 PREGNANCY

Pregnancy occurring during participation in the Add-Aspirin trial should be reported as a Notable Event on an SAE and Notable Event CRF (Form 11) and sent to the MRC CTU at UCL (in the UK) or the CRO (in India) within 24 hours of the Investigator being aware of the pregnancy. Treatment should usually be discontinued (see section 5.4.4).

Any pregnancy that occurs in a trial subject will be followed to termination or to term and the appropriate CRF completed (Form 14). Follow-up of a child born to a trial subject who received treatment in the trial during pregnancy will be as per standard clinical care. The clinical team responsible will be asked to inform the MRC CTU at UCL (in the UK) or the CRO (in India) if there is any suspicion of any adverse effect of the trial medication.

# 7.2.2 EARLY CESSATION

Any early cessations of Add-Aspirin trial treatment due to toxicity or adverse event should be reported as a Notable Event on an SAE and Notable CRF (Form 11). Forms should be sent to the MRC CTU at UCL (in the UK and Republic of Ireland) or the CRO (in India) via fax or galaxkey within 24 hours of the Investigator being aware of the event.

The clinical team responsible will be asked to inform the MRC CTU at UCL (in the UK and Republic of Ireland) or the CRO (in India) if there is any suspicion of any adverse effect of the trial medication.

# 7.3 INVESTIGATOR RESPONSIBILITIES

All non-serious ARs, whether expected or not, should be recorded in the participant's medical notes. Only aspirin related ARs should be reported in the toxicity section of the Follow-Up CRF (Form 8) at the next visit. The form should then be sent within one month to the MRC CTU at UCL (for UK and Irish participants) or entered on to the trial database (for India participants).

The MRC CTU at UCL (for UK and Irish participants) or CRO (for Indian participants) should be notified of all SAEs and SARs within 24 hours of the Investigator becoming aware of the event.

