# 7.3.1.B Severity or grading of adverse events

The severity of all AEs and/or ARs (serious and non-serious) in this trial should be graded using the toxicity grading in appendix II (CTCAE v4).

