# Table 7: Primary outcome measures

# **10.2.2** Secondary outcome measures

There are a number of secondary outcome measures that are common to all cohorts, as well as some cohort-specific outcomes, as defined in the table below. Secondary outcomes will be important for providing a comprehensive assessment of the potential health benefits and risks of the treatment. Details of outcome assessment are given in section 6. Secondary outcome measures for each cohort are defined below.

COHORT	SECONDARY OUTCOME MEASURE	
All cohorts	Overall survival	
	Time from randomisation to death from any cause	
	(note that this is the primary outcome for the gastro-oesophageal cohort)	
	Adherence	
	Based on participant-reported compliance with taking tablets.	
	During the run-in period, adherence will additionally be assessed on the	
	basis of returned blister packs and diary cards.	
	There is also a translational sub-study which will assess adherence based	
	on thromboxane $B_2$ levels measured in urine and serum samples (see	
	section 9.1 ).	
	Toxicity	
	Based on CTCAE v4	
	Serious haemorrhage	
	CTCAE (v4) grade 3 or greater	
	Serious vascular events	
	Non-fatal myocardial infarction, non-fatal stroke or vascular deaths (using	
	the definition applied by the Antithrombotics Trialists' collaboration) 	

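### Sections 6.4 and 7.3 set different collection rules for non-serious toxicity, and the rule in 7.3 makes the comparison between arms depend on a blinded judgement of cause that has no stated scale

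*Protocol*

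**What the plan says.** Table 8 (section 10.2.2) lists toxicity as a secondary outcome for all cohorts. Its whole definition is "Based on CTCAE v4", with no condition on cause.

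Section 6.4 states the collection rule as "Aspirin toxicity and adverse events will be assessed and documented at each follow-up assessment using CTCAE v4 in addition to expedited reporting of SAEs". It names no form and sets no relatedness filter. Section 6.2, on the end of the run-in, says toxicity is graded by CTCAE v4 there in the same way as at other follow-up visits. Section 7.3.1.B adds: "The severity of all AEs and/or ARs (serious and non-serious) in this trial should be graded".

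Section 7.3 gives a narrower rule. It says "All non-serious ARs, whether expected or not, should be recorded in the participant's medical notes" and then "Only aspirin related ARs should be reported in the toxicity section of the Follow-Up CRF (Form 8) at the next visit".

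Table 5 (section 7.1) defines an adverse reaction as "Any untoward and unintended response to an investigational medicinal product (IMP) related to any dose administered", whereas an adverse event includes "occurrences that are not necessarily caused by or related to that product". Section 7.1.1 counts the placebos as investigational products. Section 7.3.1.C requires a five-level causality assessment for serious events and gives none for non-serious events. Section 5.2 keeps both participants and investigators blinded.

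**The concern.** In a double-blind placebo-controlled trial, nobody has to decide what caused an event. Counting every graded event of a given type and comparing the arms estimates the excess due to aspirin. The rule in 7.3 puts an individual judgement of cause ahead of that comparison, and the person judging does not know who is taking aspirin.

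The filter is also poorly specified. An adverse reaction is already defined as related to an investigational product, and placebo is one. It is therefore unclear what the words about aspirin add, or how a blinded investigator should apply them without a scale. One site could follow 6.4 and enter every dyspepsia, bruise or minor bleed, while another follows 7.3 and enters only those it attributes.

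This is a rule about what enters the database, so a later analysis plan cannot repair it. A non-serious event judged unrelated may exist only in the medical notes. At stake is the non-serious part of the risk-benefit picture, including the dose comparison. Section 10.8.2 wants that comparison read alongside serious toxicity and other secondary health outcomes.

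**Working it through.** **Nothing to reproduce.** The protocol gives no rate, power or sample size for non-serious toxicity. The check is a side-by-side reading, then a small model of what the filter does.

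**Side by side**

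| Place | What is covered | Filter on cause |
|---|---|---|
| 6.4 | Toxicity and adverse events, each follow-up, CTCAE v4 | None stated |
| 7.3.1.B | Grading of all events, serious or not | None |
| Table 8 | Toxicity outcome, CTCAE v4 | None |
| 7.3 | Toxicity section of Form 8 | Aspirin-related reactions only |
| 7.3.1.C | Causality scale | Serious events only |

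**Inputs.** From the protocol: 9,920 randomised, two thirds to aspirin, so 9,920/3 = 3,307 on placebo and 6,613 on aspirin. Assumed, because the protocol gives no values:
- b, the background incidence of a toxicity
- e, the true excess caused by aspirin
- s, the share of aspirin-caused events judged related
- f, the share of background events judged related

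Because judgement is blinded, f is taken as equal in both arms.

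**Formulas**
- Recorded rate on placebo: f × b
- Recorded rate on aspirin: f × b + s × e
- Recorded risk difference: s × e
- Recorded risk ratio: 1 + (s/f) × (e/b)
- Power: two-proportion test, two-sided 5%, 3,307 against 6,613

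**Results**

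| b | e (points) | s | f | Placebo recorded | Aspirin recorded | Difference (points) | Ratio | Power |
|---|---|---|---|---|---|---|---|---|
| 10% | 5 | 1 | 1 | 10.0% | 15.0% | 5.0 | 1.50 | >99% |
| 10% | 5 | 0.5 | 0.5 | 5.0% | 7.5% | 2.5 | 1.50 | >99% |
| 10% | 5 | 0.7 | 0.3 | 3.0% | 6.5% | 3.5 | 2.17 | >99% |
| 10% | 5 | 1 | 0.5 | 5.0% | 10.0% | 5.0 | 2.00 | >99% |
| 5% | 1 | 1 | 1 | 5.0% | 6.0% | 1.0 | 1.20 | 53% |
| 5% | 1 | 0.5 | 0.5 | 2.5% | 3.0% | 0.5 | 1.20 | 29% |
| 5% | 1 | 0.7 | 0.3 | 1.5% | 2.2% | 0.7 | 1.47 | 67% |
| 5% | 1 | 0.9 | 0.1 | 0.5% | 1.4% | 0.9 | 2.80 | 99% |

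Rows with s = f = 1 are recording whatever the cause.

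**Reading the results**
1. The absolute excess shrinks by the factor s. It is intact only if every aspirin-caused event is attributed, and f does not enter.
2. The ratio is unchanged if s = f and inflated if s > f.
3. Power moves either way: from 53% down to 29%, or up to 67% or 99%.
4. For the dose comparison, with excesses e(100) and e(300) and the same s at both doses, the recorded difference is s × (e(300) − e(100)), so the first conclusion carries over.

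**The case against.** **The passages can be read together.** Section 6.4 opens with aspirin toxicity, speaks of documenting and names no form. Section 7.3 separates the notes from Form 8, and 7.3.1.B is about grading rather than collection. This stands in part: it is an inconsistency to reconcile, not a flat contradiction. Even on that reading, 7.3 leaves a filter with no scale and an unclear meaning under blinding, and Table 8 has no such filter.

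**Much is captured elsewhere.** This stands, and it limits the scope:
- Serious events are reported whatever the cause up to 30 days after the last treatment (7.3.1.E).
- Stops for toxicity or an adverse event go on Form 11 (7.2.2).
- Vascular and thrombotic events, diabetes, dementia and macular degeneration go on Form 10 (6.4).
- Withholding for dyspepsia is recorded on Form 8 (5.4.3.A).
- Blood counts and eGFR are scheduled to 60 months, so anaemia has a laboratory record.

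Section 10.8.2 stresses serious toxicity, above all serious haemorrhage, which is mostly outside this point.

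**Attribution may be generous.** Section 5.4.1 lists these toxicities as aspirin effects and tells investigators to manage them as if the participant were on 300mg. That may raise both s and f. A higher s reduces the loss, but a higher f does not restore any of the absolute excess.

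**Stronger readings a reader might infer.** One is that the filter simply understates aspirin toxicity, with a known loss of power. The documents do not support it. They give no attribution rate, the risk ratio need not fall, and a loss such as 53% to 29% appears when attribution is no better than chance (s = f). Another is that the filter favours one arm. Judgement is blinded, so nothing shows that it differs by arm. Events that are recorded can still be compared as randomised.

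**Conclusion.** The point holds for non-serious toxicity recorded at routine visits. Section 7.3 does not match 6.4 and Table 8. Followed as written, it makes both the aspirin-placebo and the dose comparison depend on attribution habits.

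The only firm statement about direction concerns the absolute excess: it is understated whenever some aspirin-caused events are judged unrelated, and under this model it cannot be overstated. Risk ratio and power have no fixed direction. The size is unknown. The figures above illustrate the mechanism at assumed rates and are not estimates for this trial. They also assume that background events are attributed equally in all arms.

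A reader might conclude that the trial's safety assessment as a whole is compromised. The documents do not support that, given the separate routes for serious events, early cessations, key diagnoses and blood results. Form 8 itself is not in the protocol, so it may already pre-list toxicities or carry a causality field. If so, the text of 7.3 is what needs correcting.

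**What to change.** Reconcile 7.3 with 6.4 and Table 8:
- Have the toxicity section of Form 8 record the CTCAE v4 grade of a pre-specified list of toxicities (for example dyspepsia or reflux, bleeding by site, bruising, tinnitus or hearing loss, allergic reaction) whatever the presumed cause.
- Record the investigator's attribution in a separate field, and state the scale to use for non-serious events.
- Leave non-listed, non-serious events in the medical notes, so that the load stays limited.
- Compare arms on all listed events by allocation, and show attributed events alongside.

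The cost is a wording change in 7.3, a check or small revision of Form 8, and guidance to sites. Somewhat more non-serious events would be entered per visit. No extra visits or tests are needed. If adopted mid-trial, recording would change over calendar time. The change would apply equally to all arms, but the date should be documented so that results can be shown before and after it.
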